2. ABBREVIATIONS AND DEFINITIONS

ADE	Adverse Device Effect
AE	Adverse Event
AFib	Atrial Fibrillation
AHI	Apnea-Hypopnea Index
ASV	Adaptive Servoventilation / Adaptive Servoventilator
BNP	B-type natriuretic peptide
CPAP	Continuous Positive Airway Pressure
CSA	Central Sleep Apnea
EC	Ethics Committee
eCRF	Electronic Case Report Form
EDC	Electronic Data Capture
e/hr	Events per hour
EF	Ejection Fraction
EPAP	Expiratory Positive Airway Pressure
FDA	Food and Drug Administration
HF	Heart Failure
HFpEF	Heart failure with preserved ejection fraction; LVEF \geq 50%
HFrEF	Heart failure with reduced ejection fraction
IDE	Investigational Device Exemption
IRB	Institutional Review Board
KCCQ	Kansas City Cardiomyopathy Questionnaire
LV	Left Ventricular
LVEF	Left ventricular ejection fraction
MI	Myocardial infarction
NT pro-BNP	N-terminal prohormone of b-type natriuretic protein
ODI	Oxygen Desaturation Index
OSA	Obstructive Sleep Apnea
PAP	Positive Airway Pressure
SAE	Serious Adverse Event
SC	Steering Committee
SDB	Sleep-Disordered Breathing, also referred to as sleep apnea
SOP	Standard Operation Procedures
TIA	Transient ischemic attack

4. PROTOCOL SUMMARY

Objectives	Demonstrate feasibility of study conduct and that acceptable adherence to ASV therapy can be achieved in recently hospitalized HFpEF patients with moderate to severe SDB.
Study Design	This study is a prospective, single-arm, unblinded, multi-center study. All subjects meeting criteria will receive adaptive servo-ventilation (ASV).
Number of Subjects	The study will aim to enroll 160 evaluable subjects. For the purposes of this study, an evaluable subject is one with ASV usage of at least 4hrs per night for 70% of the study nights, excluding nights hospitalized at 30 days after study entry. In order to achieve 160 evaluable subjects it is estimated that up to 300 subjects will be initially enrolled in the study.
Selection criteria	
Inclusion criteria for the study are:
 
 1. Patients 18 years or older 2. Patients with heart failure with preserved ejection fraction (HFpEF; LVEF $\geq 50\%$) 3. Hospital admission or equivalent (such as ER visit alone or clinic visit alone) and acute decompensated HF as determined by: 
 a. Dyspnea at rest or with minimal exertion AND b. Treatment with at least one dose of IV diuretic or ultrafiltration AND c. At least two of the following signs and symptoms: 
 i. Orthopnea ii. Pulmonary rales that do not clear with cough iii. Congestion on chest X-ray iv. Local BNP or NT pro-BNP level: 
 A. No current atrial fibrillation (AFib): BNP ≥ 100 pg/mL or NT pro-BNP ≥ 300 pg/mL OR B. Current AFib: BNP ≥ 150 pg/mL or NT pro-BNP ≥ 450 pg/mL 4. Sleep disordered breathing (SDB) documented by screening polygraphy with an AHI ≥ 15 events/hour (e/hr) 5. Patient is able to fully understand study information and sign informed consent 
Exclusion criteria for the study are:
 
 1. Right-sided heart failure without left-sided failure 2. Current chronic use (within 4 weeks of study entry) of any PAP therapy (eg, CPAP, APAP, or bi-level) or contraindicated for PAP therapy

	
 3. Sustained systolic blood pressure <80 mmHg at baseline 4. Complex congenital heart disease 5. Constrictive pericarditis 6. Chronic hypoxemia as evidenced by sustained oxygen saturation ≤ 85% at rest during the day or at start of nocturnal oximetry recording or regular use of oxygen therapy (day or night) 7. Transient ischemic attack (TIA) or Stroke within 3 months prior to study entry 8. Definite clinically evident acute myocardial infarction within 3 months of study entry 9. Known amyloidosis, hypertrophic obstructive cardiomyopathy, or arteriovenous fistulas 10. Moderate or greater valvular heart disease as the primary reason for heart failure 11. Pregnant, or planning to become pregnant during the study period 12. In the opinion of the investigator, the index acute decompensated HF event was due primarily to uncontrolled AFib with fast ventricular response rate 13. Inability to comply with planned study procedures
Primary Endpoints	ASV Adherence rate (average hours used per day) at 3 months
Secondary Endpoints	
 • Feasibility of study conduct as measured by recruitment rate (subjects enrolled per month) by site, reasons for screen failures, and where in the hospital system patients are recruited (eg, HF clinic, general cardiology, etc) • Change in quality of life as measured by the Kansas City Cardiomyopathy Questionnaire (KCCQ-12) • Number of hospitalizations for any reason following study entry • Death for any reason during study participation
Scheduled follow up	
For evaluation of the primary and secondary endpoints, subjects will be followed for a period of 3 months (12 weeks).
 
 • Visit 1 will occur at baseline for device set-up and KCCQ-12 • Visit 2 will occur at 12 weeks for disposition of device, KCCQ-12, and determination of hospitalizations and death

5. INTRODUCTION

5.1. Background Information

Heart failure (HF) continues to present a social and economic burden, especially with regard to HF hospitalizations. The current HF treatment guidelines^{1,2} include a number of treatments focused on HF with reduced ejection fraction (HFrEF; left ventricular ejection fraction [LVEF] $\leq 45\%$), but no evidence-based therapies for HF with preserved ejection fraction (HFpEF; LVEF $\geq 50\%$).

Sleep-disordered breathing (SDB) is very common in HF populations that have reduced as well as preserved ejection fraction, with reported prevalence rates of 50-75%^{3,4,5}. There are very few studies that have evaluated the impact of treating SDB in HFpEF, and the studies that do exist generally include a small number of patients⁶.

The Adaptive Servo-Ventilation for Central Sleep Apnea in Systolic Heart Failure Study (SERVE-HF) showed that ASV in patients with stable HFrEF and SDB with predominant central sleep apnea increased cardiovascular mortality⁷. The results of secondary multistate modeling analysis showed that the risk of direct sudden cardiovascular death and hospitalization for worsening HF were associated with poor left ventricular function that attenuated as the LVEF approached normal⁸.

Cardiovascular Improvements with Minute Ventilation-targeted ASV Therapy in Heart Failure Study (CAT-HF) was a randomized controlled clinical trial in the United States and Germany. It was designed to evaluate the effect of ASV in hospitalized heart failure (HFrEF and HFpEF) patients on a global rank endpoint of survival free from CV hospitalization and improvement in functional capacity measured by 6-minute walk distance. Analysis of the 126 subjects that were randomized showed a neutral result for the primary endpoint; however, in the pre-specified analysis of the primary endpoint by LVEF strata, there was a favorable statistically significant difference in the HFpEF subgroup ($p=0.036$) (*O'Connor in press*). There was no safety signal for increased mortality risk in patients randomized to ASV.

CAT-HF demonstrated that SDB can be effectively controlled by ASV in a HF population; however, adherence to ASV was very low, limiting the ability to determine the effect of ASV on HF outcomes. Despite this, analysis showed improved outcomes with ASV therapy in the HFpEF subgroup (*O'Connor in press*). Newer technologies include the web-based AirView system, which allows the patient's care team to monitor adherence, and the myAir application, which provides patients with immediate feedback on their actual therapy use. These have been shown to improve adherence by addressing issues with therapy as they arise, thus increasing patient engagement and adherence to therapy⁹.

Although the CAT-HF study showed a positive signal in the HFpEF subgroup, these patients represented a small percentage of the randomized subjects in the study. The current study aims to show that by applying newer technologies to support adherence, as well as focusing on the lessons learned in CAT-HF to identify and recruit HFpEF patients, acceptable adherence to ASV therapy can be achieved in HFpEF patients. Demonstrating feasibility of study conduct in this way will help support a future phase III randomized controlled trial with morbidity and mortality endpoints.

5.2. Intended Use

The AirCurve 10 ASV device is indicated for the treatment of patients weighing more than 66 lb (30 kg) with obstructive sleep apnea (OSA), central and/or mixed apneas, or periodic breathing. It is intended for home and hospital use. The humidifier is intended for single patient use in the home environment and re-use in a hospital/institutional environment.

Contraindications

ASV therapy is contraindicated in patients with chronic, symptomatic heart failure (NYHA II-IV) with reduced left ventricular ejection fraction (LVEF \leq 45%) and moderate to severe predominant central sleep apnea.

Positive airway pressure therapy may be contraindicated in some patients with the following pre-existing conditions:

- severe bullous lung disease
- pneumothorax or pneumomediastinum
- pathologically low blood pressure, particularly if associated with intravascular volume depletion
- dehydration
- cerebrospinal fluid leak, recent cranial surgery, or trauma.

6. STUDY OBJECTIVES

The objective of the study is to demonstrate feasibility of study conduct, and to evaluate adherence to ASV therapy at 3 months in HFrEF patients diagnosed with moderate to severe sleep apnea. Adherence will be monitored using cloud-based technology in which data from each ASV machine is automatically transmitted to a secure, HIPAA-compliant system (AirView). The system is accessible through the internet with a secure interface. This technology can be customized to “flag” patients who do not meet criteria for minimal use. Data will be reviewed by each site’s respiratory/sleep team, and in patients where the use of ASV is less than 3 hours per night, the respiratory/sleep team will contact the patient to troubleshoot the reasons for low usage, and provide appropriate solutions. In addition, a central Adherence Core Lab will oversee the ASV usage at all sites, providing guidance and support where necessary.

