7. STUDY DESIGN

The CAT-PEF Feasibility Study is a prospective, single-arm, unblinded, multi-center, study of HFrEF subjects diagnosed with SDB using ASV therapy.

This study will be conducted in up to 10 centers in the US and Germany.

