7.2.3. Subject Inclusion Criteria

1. Patients 18 years or older
2. Patients with heart failure with preserved ejection fraction (HFpEF; LVEF $\geq 50\%$)
3. Hospital admission or equivalent (such as ER visit alone or clinic visit alone) and acute decompensated HF as determined by:
 - a. Dyspnea at rest or with minimal exertion
AND
 - b. Treatment with at least one dose of IV diuretic or ultrafiltration
AND
 - c. At least two of the following signs and symptoms:
 - i. Orthopnea
 - ii. Pulmonary rales that do not clear with cough
 - iii. Congestion on chest X-ray

- iv. Local BNP or NT pro-BNP level:
 - A. No current atrial fibrillation (AFib): BNP \geq 100 pg/mL or NT pro-BNP \geq 300 pg/mL
OR
 - B. Current AFib: BNP \geq 150 pg/mL or NT pro-BNP \geq 450 pg/mL
4. Sleep disordered breathing (SDB) documented by screening polygraphy with an AHI \geq 15 events/hour (e/hr)
5. Patient is able to fully understand study information and sign informed consent

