10.4. Screening Procedures

Patients who have been admitted to the hospital, or in the outpatient setting, if within 14 days of discharge, and have symptoms of acute decompensated heart failure will first be evaluated for eligibility for the study based on chart review.

Review the patient's records to ensure the following:

1. Evidence of HFpEF ($EF \geq 50\%$) that is not solely right-sided. HFpEF is based on most recent echocardiogram results, but must be within last 12 months.
2. This (or the most recent) hospitalization includes acute decompensated HF as determined by dyspnea and other signs and symptoms as listed in inclusion criteria.
3. The first healthcare encounter related to this hospitalization (e.g., ER, cath lab) was at least 24 hours and no more than 14 days prior to consent.

If the patient appears to be eligible based on the cardiology-related entry criteria, they may be approached about study participation. A brief interview may be conducted to further address potential eligibility criteria.

If the patient continues to appear to be eligible for participation in the study then consent will be obtained. A log of patients screened but not eligible for the study will be maintained.

NOTE: All subjects who sign a consent form must be entered in the data management system, whether or not they are entered into the study.

1. Document demographics and eligibility criteria data
2. Arrange for AHI measurement using the ApneaLink overnight. Subject is not eligible for study entry if $AHI < 15$ e/hr from ApneaLink.
3. If $AHI \geq 15$ e/hr with ApneaLink Air and other entry criteria are met, confirm tolerability of the mask and ASV therapy by having the subject use the system for a short time (awake or asleep).
4. If they are not eligible for study entry, document the reason for screen failure in the data management system.

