13. STATISTICAL ANALYSIS

This study aims to evaluate the adherence to ASV therapy in HFrEF patients with moderate to severe SDB. Descriptive summaries, including means, standard deviations, medians, 25th, and 75th percentiles will be presented for continuous variables; the number and frequency of subjects in each category will be presented for nominal variables. Analyses will be performed using SAS Version 9.3 or later.

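### Does calling the study population HFrEF in Sections 6, 7 and 13 leave the trial with the wrong target population?

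*Combined protocol and SAP*

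**What the plan says.** Three sections name patients with reduced ejection fraction:

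- Section 6 gives the aim as "to evaluate adherence to ASV therapy at 3 months in HFrEF patients diagnosed with moderate to severe sleep apnea".
- Section 7 describes the trial as a "study of HFrEF subjects diagnosed with SDB using ASV therapy".
- Section 13 opens with "This study aims to evaluate the adherence to ASV therapy in HFrEF patients with moderate to severe SDB".

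Other sections name patients with preserved ejection fraction:

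- The objective in the Section 4 summary is to show that "acceptable adherence to ASV therapy can be achieved in recently hospitalized HFpEF patients with moderate to severe SDB".
- The background in Section 5.1 states the aim as showing that "acceptable adherence to ASV therapy can be achieved in HFpEF patients".
- Inclusion criterion 2 in Section 7.2.3 reads "Patients with heart failure with preserved ejection fraction", with LVEF of at least 50%.
- Section 10.4 makes an EF of at least 50% the first chart-review check and adds that "HFpEF is based on most recent echocardiogram results, but must be within last 12 months".

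The two labels are not synonyms. Section 2 expands them differently, and Section 5.1 puts HFrEF at LVEF of 45% or less and HFpEF at 50% or more.

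**The concern.** The label appears in the formal objective, the design statement and the opening sentence of the only statistical section, so it is not confined to background text. The two populations do not overlap. Taken at face value, the objective concerns patients of whom the trial will have none, and the data could not answer it.

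The label is also an awkward one to get wrong. Section 5.1 reports that ASV raised cardiovascular mortality in stable HFrEF with predominantly central apnea. Section 5.2 states that "ASV therapy is contraindicated in patients with chronic, symptomatic heart failure (NYHA II-IV) with reduced left ventricular ejection fraction", at LVEF of 45% or less and with moderate to severe predominant central sleep apnea. The sleep criterion is an AHI of at least 15 with no restriction on apnea type. A reader of Sections 6 and 7 alone might conclude that the trial plans to treat a group that includes patients for whom the protocol's own labelling text contraindicates the device. If that were so, both the validity of the objective and the safety of subjects would be at stake.

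**Working it through.** The question is whether anything the trial does depends on the label. Four steps could depend on it.

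**1. Who enters.** Entry is governed by Sections 7.2.3, 7.2.4 and 10.4, not by the aim sentence. Section 10.1 requires every inclusion criterion to be met and no exclusion criterion. Criterion 2 sets LVEF at 50% or more, and no other criterion admits a lower value. The number of eligible subjects with EF below 50% is therefore zero, whatever Sections 6, 7 and 13 call the population.

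**2. Who is treated.** Section 7.1 requires all eligibility criteria to be confirmed before a device is dispensed. The Section 5.2 contraindication needs three things together: LVEF of 45% or less, NYHA class II to IV, and moderate to severe predominant central apnea. The EF criterion removes the first, so apnea type no longer bears on it. Exclusion 2 separately bars patients contraindicated for PAP therapy.

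**3. What is analysed.** Section 13.2 estimates mean usage with its 95% confidence interval. Section 13.3 estimates the mean KCCQ-12 change and the mean number of hospitalizations per subject. None of these selects or stratifies by ejection fraction. An analyst who did restrict to HFrEF would get an empty data set and see the slip at once.

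**4. What the sample size rests on.** Inputs from Section 13.1: 160 evaluable subjects, SD 1.6 hours per night, 95% confidence, stated margin 0.25 hours or less, 60% evaluable.

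- Half-width, normal quantile: 1.96 × 1.6 / √160 = 0.248 hours.
- Half-width, t quantile on 159 degrees of freedom: 1.975 × 1.6 / √160 = 0.250 hours (0.2498 before rounding).
- Enrolment: 160 / 0.60 = 266.7, against 266 stated and rounded up to 300.

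The stated margin is reproduced, and the enrolment figure agrees to within one subject. The label does not enter either formula. The SD is taken from a study of the myAir application and is not presented as an HFrEF or HFpEF value.

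**Count of aim and design statements.** Five statements of the aim or design name an EF population: the Section 4 objective, the Section 5.1 aim, and Sections 6, 7 and 13. Three say HFrEF and two say HFpEF. Every statement that sets an entry threshold (Sections 4, 7.2.3 and 10.4) says 50% or more. The rationale in Section 5.1 is built on the HFpEF subgroup of CAT-HF, and the study's own name, CAT-PEF, fits that.

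**The case for a change.** The strongest argument for acting is that an ethics committee approves this document and investigators are bound by it, so it should not state two incompatible populations. Nothing within Section 13 corrects its opening sentence. Because the error occurs three times, mending one place would leave the others. The correction would cost three words.

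What stands is that the text contradicts itself and the passages ought to be reconciled if the document is reopened for another reason. An error in reading the PDF is an unlikely explanation for three separate occurrences.

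What does not stand is the consequence. The data do answer the study question, because the question is stated for HFpEF in the summary and background, and HFpEF patients are the ones enrolled. The safety argument fails on the protocol's own terms: if no subject with EF below 50% is eligible, the aim sentence does not expose a reduced-EF group to treatment. A site that went by Section 7 alone would still meet the EF check at chart review and again when confirming eligibility. An entry error would be an entry-criteria deviation, and Section 15.2 provides for listing these and evaluating significant ones before database lock.

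**Conclusion.** No change to the plan follows. The HFrEF wording in Sections 6, 7 and 13 is best read as one drafting slip repeated three times. The intended population is clear from the summary, the rationale, the eligibility criteria and the screening steps. Its effect on enrolment, treatment, endpoints, analysis and sample size is nil, and the half-width stays at about 0.25 hours per night with 160 evaluable subjects. A report writer would describe the population by who was enrolled.

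This rests on two assumptions: that sites apply the eligibility criteria as written, and that the most recent echocardiogram, which may be up to 12 months old, still reflects a subject's ejection fraction at entry. Neither depends on the label, and rewording the three sentences would not affect either.

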7. STUDY DESIGN

The CAT-PEF Feasibility Study is a prospective, single-arm, unblinded, multi-center, study of HFrEF subjects diagnosed with SDB using ASV therapy.

This study will be conducted in up to 10 centers in the US and Germany.

7.1. Enrollment

Subjects will be recruited from in-patient clinical services or in the outpatient setting if within 14 days of discharge. If a subject is willing to participate in the CAT-PEF Feasibility Study, a written

informed consent for the study must be obtained prior to any study related procedure. Before dispensing a device, all eligibility criteria must be confirmed.

7.2. Selection of subjects

7.2.1. Informed Consent

The consent form is written in accordance with applicable data privacy acts and FDA Regulations and approved by the responsible Institutional Review board (IRB)/Ethics Committee (EC).

The investigator or responsible staff will explain the nature, purpose and risks associated with the study. The patient will be given sufficient time to consider the study's implications before deciding whether to participate. Information materials created by the investigators and Sponsor must be approved by the responsible IRB/EC prior to use.

A signed, IRB/EC-approved consent form must be obtained from the patient prior to the performance of any protocol-related testing or procedures unless obtained as part of standard care. The consent process must be performed by a designated clinical study team member authorized by the IRB/EC to consent patients and listed on the Delegation of Authority Log as having privileges to consent patients. A signed copy of the consent form must be maintained in the study files and a copy provided to the patient. The patient's permanent medical records should indicate study participation.

7.2.2. Number of Subjects

Up to 300 subjects will be initially enrolled in this study. For endpoint evaluation, 160 evaluable subjects are required. For the purposes of this study, an evaluable subject is one with ASV usage of at least 4hrs per night for 70% of the study nights, excluding nights hospitalized after 30 days (1 month) of ASV usage.

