9. THERAPY

9.1. Treatment with Adaptive Servo-ventilation (AirCurve)

The AirCurve device will be used at home; however the therapy can be initiated in the hospital or as an outpatient within 14 days of hospital discharge. Although the AirCurve has three therapy modes, CPAP, ASV, and ASVAuto, only the ASVAuto mode will be used for this study. Subjects are advised to use the AirCurve device during any significant sleeping period, including naps. Ideally, AHI should be at or below 5 e/hr. However, if the AHI cannot be maintained below 10 e/hr, the subject's therapy should be adjusted (mask and/or pressure settings).

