10.6. Overview of visits

	Screening	Baseline "Day 0" (≤3 days from AL report)	2-3 days Post-device start	30 days (±2 days) "1 mo"	Weekly during study	12 weeks (±2 weeks) "3 mo"
Visit Location:	Hospital or Clinic	Hospital or Clinic	Phone call			Clinic or Phone Call
Review of HF history, signs & symptoms	X					
ApneaLink Air test	X					
ASV therapy and mask tolerance	X					
KCCQ-12	X					X
Initiation of ASV Therapy		X				
ASV Device use monitoring			X	X*	X	X

*Check to confirm adequate device use

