11.5. Subject Discontinuation Criteria

If, after 30 days after initiation of therapy, a subject has not met the adherence criteria of at least 4hrs ASV usage per day (24hr period) for 70% of the days enrolled (excluding days spent in the hospital), they will be discontinued from the study. Follow procedures for Device and Subject Disposition in Section 11.6. Record the number of hospitalizations and date of discontinuation on the end of study eCRF.

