13.1. Justification of the Sample Size

The sample size has been determined to estimate the primary objective (the mean usage in hours per night) with sufficient precision. A sample size of 160 evaluable subjects yields a margin of error equal to 0.25 hours per night or less, when the confidence level is 95% and the standard deviation of usage is 1.6 hours per night or less (as observed in a similar study of myAir⁹). Subjects not meeting the evaluability criteria of at least 4hrs ASV usage per day (24hr period) for 70% of the days enrolled (excluding days spent in the hospital) within the first 30 days of therapy initiation, will be discontinued from the study. Assuming that 60% of the study subjects will be evaluable, 266 (which can be rounded up to 300) subjects are expected to be initially enrolled in the study.

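### Does stating the 4-hour, 70% rule per night in some sections and per 24-hour day in others give the study two definitions of an evaluable subject?

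*Combined protocol and SAP*

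**What the plan says.** The rule appears in four places.

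- The Protocol Summary (Section 4) gives it as "ASV usage of at least 4hrs per night for 70% of the study nights, excluding nights hospitalized at 30 days after study entry".
- Section 7.2.2 uses the same night-based unit, saying that "an evaluable subject is one with ASV usage of at least 4hrs per night for 70% of the study nights", and ends with "excluding nights hospitalized after 30 days (1 month) of ASV usage".
- Section 11.5, which discontinues subjects, requires "at least 4hrs ASV usage per day (24hr period) for 70% of the days enrolled (excluding days spent in the hospital".
- Section 13.1 refers to "Subjects not meeting the evaluability criteria of at least 4hrs ASV usage per day (24hr period) for 70% of the days enrolled", assessed "within the first 30 days of therapy initiation", and says that these subjects leave the study.

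Section 9.1 adds that "Subjects are advised to use the AirCurve device during any significant sleeping period, including naps". No section defines the hours of a night. The visit table in Section 10.6 describes the 30-day review only as "Check to confirm adequate device use".

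**The concern.** Read literally, the sections use two units. If a night means the overnight sleep period alone, a subject who sleeps a little under 4 hours on the device and adds a nap passes the 24-hour version and fails the night version. That subject would be kept in the study under Section 11.5 and yet not be evaluable under Section 7.2.2.

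The rule matters because it decides at day 30 who is discontinued and who counts toward the 160 subjects required for endpoint evaluation. It also fixes the evaluable share to be compared with the 60% assumed in Section 13.1. Two smaller differences accompany it: the 30-day clock starts at study entry in the Protocol Summary but at therapy start elsewhere, and the hospital exclusion is phrased awkwardly in Section 7.2.2.

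**Working it through.** **The four statements side by side**

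| Section | Hours counted per | Denominator | Clock starts at | Role of the statement |
|---|---|---|---|---|
| 4 (Summary) | night | study nights | study entry | describes the target number |
| 7.2.2 | night | study nights | ASV usage | describes the target number |
| 11.5 | 24-hour day | days enrolled | therapy initiation | discontinues subjects |
| 13.1 | 24-hour day | days enrolled | therapy initiation | names the rule as evaluability, sizes the study |

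The two sections that apply the rule match in unit, denominator and start. Section 13.1 attaches the word evaluability to the 24-hour version, so a subject retained under Section 11.5 is evaluable under Section 13.1. A mismatch arises only if Section 7.2.2 is applied as a separate test with a night defined to exclude daytime use, and no section gives that definition.

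Usage elsewhere points the same way. The Protocol Summary states the primary endpoint in hours per day, while Section 13.1 calls the same quantity hours per night and uses both units in one paragraph. Section 9.3 lists usage hours from AirView without splitting night from daytime.

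**The plan's own figures.** Inputs from Section 13.1: n = 160, SD 1.6 h, 95% confidence, 60% evaluable.

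- Half-width: 1.96 × 1.6 / √160 = 0.248 h (0.2498 h with the t quantile), against the stated 0.25 h.
- Enrolment: 160 / 0.60 = 266.7, against the stated 266, rounded up to 300.

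Neither calculation depends on whether the threshold is counted by night or by day.

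**Where the unit could matter.** Over 30 days the cut-off is 0.70 × 30 = 21. A subject with 20 qualifying nights has 20/30 = 66.7% and fails; one more day lifted to 4 h by a nap gives 21/30 = 70.0% and passes. Only subjects close to the cut-off on both hours and days are exposed.

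**Bound on the target.** With 300 enrolled, 160 evaluable needs 160/300 = 53.3%. At 60%, 0.60 × 300 = 180 are evaluable, so there are 180 − 160 = 20 to spare, which is 20/300 = 6.7 percentage points. The margin is relevant only if the 60% was set on the 24-hour count and the night count were then applied. In the other direction the share can only rise.

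**Start date and hospital wording.** Section 10.6 places therapy initiation at Day 0, so study entry and therapy start nearly or exactly coincide. In Section 7.2.2 the 30-day phrase most naturally dates the assessment, because excluding only nights in hospital after day 30 would have no bearing on a 30-day check.

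**Hospital days left uncounted.** Over 30 nights with 20 qualifying, missing one hospital night changes nothing (20/29 = 69.0%, still a fail), and missing two does (20/28 = 71.4%). The ±2 days in Section 10.6 is a visit window; no section makes it the denominator, and Section 13.1 confines the rule to the first 30 days.

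**The case for a change.** The strongest case is that the 24-hour parenthesis in Sections 11.5 and 13.1 looks deliberate and has no counterpart in Section 7.2.2. With up to 10 centres, a rule that removes subjects should not be open to different readings. An illustration with assumed inputs (mean night use 5 h, between-subject SD 1.6 h, night-to-night SD 1.5 h, 30 days) has 57% passing on night use alone, against 63%, 69% and 79% if naps add 0.25, 0.5 or 1 h every day. The step from 63% to 57% lies within the 6.7-point margin; the step from 69% to 57% does not.

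It stands that the wording differs and that a literal reader could find two rules. The illustration shows that the unit would matter if every subject napped on the device every day and a night-only count were enforced. The documents support neither condition: they give no nap data, and the section that discontinues subjects states the 24-hour count expressly.

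A second objection is that hospital days must be excluded at day 30, while Sections 10.5.3 and 12.1 schedule hospitalization data for the end of the study. Section 11.5 nevertheless requires the exclusion when the rule is applied, so a site following it has to establish those days. The weekly AirView review and contacts about low use (Section 10.5.2, Appendix I) can bring an admission to light, although they do not count nights. How the days are recorded is operational detail that the eCRF or Manual of Procedures, neither of which is among the documents, may cover.

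**Conclusion.** The wording is inconsistent, but two working definitions are not established. A team applying Sections 11.5 and 13.1 as written has one unit, one denominator and one start date, and the retained subjects are the evaluable ones. The stated 160, 0.25 h and roughly 266 stand. The number of subjects whose status turns on the unit cannot be computed and is probably small, and the 160 is at risk only if more than 20 of 300 lose evaluable status.

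This rests on reading night as loose usage for the daily device record, which the plan's mixed use of the two words supports but does not state. It also rests on sites looking up hospital days at the 30-day review, as Section 11.5 implies.

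Because the rule governs discontinuation, the four statements must be reconciled when the text is next edited. Which wording holds is for the sponsor to decide. That is clerical tidying: it alters no design figure or analysis and does not call for an amendment of its own.
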